15.1. INSTITUTIONAL REVIEW BOARD (IRB)/ETHICS COMMITTEE (EC)

IRB/EC approval will be obtained at each of the investigational sites prior to enrolling clinical investigation subjects at that site. In addition, any SADE, UADE or serious incident that meets the reporting criteria of the IRB/EC, will be reported to the IRB/EC. During the clinical investigation, the Investigator should promptly provide written reports to the IRB/EC of any changes that affect the conduct of the clinical investigation and/or increase risk to the subjects, unless otherwise submitted by the Sponsor.

15.2. INFORMED CONSENT

The Investigator, or qualified clinical investigation personnel designated to perform this task, will explain the nature of the clinical investigation to the subject, and answer all questions regarding participation in this clinical investigation. Prior to any clinical investigation procedures being performed, the ICF will be reviewed, signed and dated by the subject, and by the person administering the informed consent. A copy

. .

of the ICF will be given to the subject, and the original will be placed in the subject's clinical investigation records. Subjects will need to sign updated versions of the ICF if required by the Investigator's IRB/EC during the course of the clinical investigation.

16. Data Collection Process

The Sponsor will collect clinical data for this clinical investigation utilizing eCRFs through an EDC system. All clinical data is entered into the EDC system by designated personnel at each of the Investigator sites. All data entered in the eCRFs are supported by source documentation.

17. Clinical Investigation Monitoring

It is the responsibility of the Site Principal Investigator to oversee the safety of the clinical investigation at his/her site, to include the careful assessment and appropriate reporting of AEs/incidents as noted above as well as the implementation of site data safety. The Sponsor, or designee, will monitor the sites to ensure informed consent has been documented appropriately, to ensure the information documented on the completed case report forms match the medical records and to resolve any differences. The Sponsor will take all steps necessary to ensure data integrity. The Sponsor will also review significant new information, including unanticipated adverse device effects/incidents and ensure that such information is provided to all Investigators, their IRBs/ECs, and applicable regulatory authorities. Additionally, a quality assurance check will be performed to ensure the investigator is complying with the Clinical Investigation Plan and applicable regulations in the collection of all clinical investigation data.

18. Data Handling and Record Keeping

Information about clinical investigation subjects will be kept confidential. In the event a subject revokes authorization to collect or use protected health information, the Site Investigator, by regulation, retains the ability to use all information collected prior to the revocation of subject authorization. The Health Insurance Portability and accountability Act (HIPAA) will apply in order to ensure data protection and document anonymization. Records are to be stored in a secure location. Retention of records shall be maintained through the clinical investigation duration as well as specified years following the clinical investigation completion as required by local regulatory authority.

19. Reports

Analysis will be executed and interim reports will be prepared on a yearly basis. Upon the completion of all subjects final post-operative assessment, data freeze will take place and the final report will be prepared.

20. Public Registration

The clinical investigation and summary of results will be registered on ClinicalTrials.gov and/or European Database on Medical Device (EUDAMED).

21. Completion of the Clinical Investigation

The Investigator will conduct this clinical investigation in compliance with the Clinical Investigation Plan, and will complete the clinical investigation within the timeframe specified in the contract.

Continuation of the clinical investigation beyond this time must be mutually agreed upon in writing by both the Investigator and Stryker. The Investigator will provide a summary of the clinical investigation results in accordance with the IRB/EC guidelines.

Stryker may terminate this clinical investigation prematurely, either in its entirety or at this site, for reasonable cause provided that written notice is submitted a reasonable time in advance of the intended termination. The Investigator may also terminate the clinical investigation at their site for reasonable cause, after providing written notice to Stryker a reasonable time in advance of the intended termination. If Stryker terminates the clinical investigation for safety reasons, it will immediately notify the Investigator by telephone and subsequently provide written instructions for clinical investigation termination.

22. Essential Documents

All essential documentation will be stored as specified under the Sponsor's Standard Operating Procedures.

23. Publication Policy

Refer to the clinical investigation agreement for the publication policy.

24. References

1.1. LIST OF ABBREVIATIONS

Acronym	Definition
ADE	Adverse Device Event
AE	Adverse Event
CI	Confidence Interval
CIP	Clinical Investigation Plan
CRF	Case Report Form
eCRF	Electronic Case Report Form
EC	Ethics Committee
EDC	Electronic Data Capture
EU MDR	European Medical Device Regulation
FR	Final Report
ICF	Informed Consent Form
ICH-GCP	International Conference of Harmonisation Good Clinical Practice
IFU	Instructions for Use
ITT	Intent-to-Treat
Intra-Op	Intra-Operative
IR	Interim/Annual Report
IRB	Institutional Review Board
LTFU	Lost to Follow-Up
MCS	SF-36 Mental Component Summary
PCS	SF-36 Physical Component Summary
PP	Per Protocol
Pre-Op	Pre-Operative
SADE	Serious Adverse Device Effect
SAE	Serious Adverse Event
SAP	Statistical Analysis Plan
SF-36v2	36-Item Short Form Health Survey
UADE	Unanticipated Adverse Device Effect

1.2. STATISTICAL ANALYSIS PLAN REVISION HISTORY

Version	Effective Date	Description	Reason
1	25MAR2020	Initial Version	
2	24JUL2020	Adjustment chapter 4.4 Timing of Outcome Assessment	CIP changes, merge of Pre-Operative and Operative/ Discharge visit.
3	23JUL2021	Distinction interim/final Analysis Amendment Table Templates section 7	Revision DQI 20-048, CIP V3

	CIP 2.2	changes:	chapter	

2.1. BACKGROUND AND RATIONALE

The T2 Tibia Nailing System represents the latest and most comprehensive development of the original intramedullary principles presented by [name] in 1940. As an addition to the T2 Nailing System, Stryker has created a new generation tibial implant that offers an efficient treatment option for multiple indications. The T2 Alpha Tibia Nail includes new locking options and the ability to utilize the advanced locking screw which creates an axial and angular stable construct. New instrumentation offers a combination of innovation, simplicity and efficiency that is designed to suit the various needs of surgeons and OR staff.

The T2 Alpha Tibia Nailing System is fully integrated into the T2 Alpha Platform. The system includes two approaches: infrapatellar approach and suprapatellar approach and allows for multiple locking configurations for stable fixation. This clinical investigation will evaluate the safety and efficacy/performance of the T2 Alpha Tibia Nailing System.

2.2. CLINICAL INVESTIGATION DESIGN

This investigation is a prospective, multicenter clinical investigation. It is anticipated that a total of 80 subjects will be enrolled at up to 5 sites. Enrollment is estimated to commence in Q4 of 2018. Neither subjects nor investigators are blinded to treatment and the clinical investigation includes a historical control which will be compared to the T2 Alpha Tibia Nailing System.

The enrollment period is expected to occur over 32 months. Total duration of enrollment, 12 month follow-up and analysis is expected to take 47 months. The clinical investigation has been designed to follow the surgeon's standard of care for tibia fractured subjects, in addition to a 12 month follow-up visit.

3. Research Goals

3.1. FRAMEWORK

All quantitative variables, including those based on calculations (secondary elements), will be analyzed with a case summary evaluation before the detailed characteristics and parameter can be evaluated. A case summary contains a listing of the number of valid cases/values, missing cases/values (if any) and total cases/values in the specific analysis. In general, as central position parameter for quantitative

variables the mean and median will be analyzed. As variation parameter the standard deviation, 95% confidence interval of the mean, interquartile range and maximum and minimum will be calculated. All quantitative variables will be assessed for normality used the Shapiro-Wilk test. For optional visualization of quantitative variables, box-and-whisker plots will be used. Additional analyses like skewness and kurtosis measures of standard errors are also optional.

All qualitative variables, including those based on summaries (secondary elements), will be analyzed listing the proportions, frequencies, column and row totals and missing proportion (if any).

3.1.1. Primary Analysis / Endpoint

This analysis is only part of the final report. The primary endpoint analysis will only be executed once at the end of the clinical investigation and will not be part of any interim or annual reports or presentations given in front of the final report.

The 12 months post-operative results for subjects implanted with the T2 Alpha Tibia Nailing System will be compared to Sanders et al: Semiextended intramedullary nailing of the tibia using a suprapatellar approach: radiographic results and clinical outcomes at a minimum of 12 months follow-up. J Orthop Trauma, 2014; Sun et al: The outcome comparison of the suprapatellar approach and infrapatellar approach for tibia intramedullary nailing. Int Orthop, 2016; and Chan et al: Suprapatellar Versus Infrapatellar Tibial Nail Insertion: A Prospective Randomized Control Pilot Study. J Orthop Trauma, 2016". Specifically, the SF-36 score results reported by Wang, et al. (2017), Sanders, et al. (2014), Sun, et al. (2016) and Chan, et al. (2016) will serve as the control groups for the T2 Alpha Tibia group.

Higher SF-36 PCS and MCS score results are linked to better subject results and vice versa.

The clinical investigation endpoint is non-inferiority to the control, meaning the clinical investigation result should be equal or better than the control. In this clinical investigation, an equal or better SF-36 score result means equal or greater (\geq). As only results from samples will be captured, results are mostly estimates of the true population parameter. These estimates vary by a certain area, where it is expected that the true population parameter falls within. Based on this, it is required to specify a lower limit for the acceptable difference or zone of indifference, denoted as - θ .

Hypotheses were developed to allow for a comparison of the 12 months post-operative SF-36 PCS to evaluate effectiveness / performance. The 12 months post-operative SF-36 PCS is the primary endpoint of this clinical investigation. Hypothesis tests will be one-sided with a significance level α of 5%.

Hypothesis	Equations	Interpretation	
Null (H ₀)	$A - B < -\theta$	Central tendency of A is inferior to	
	12 Alpha 11bia (A) – Control (B, pooled benchmark results) < $-\theta$	the central tendency of B.	
Alternative	$A - B \ge -\theta$	Central tendency of A is non-inferi	
(H ₁)	T2 Alpha Tibia (A) - Control (B, pooled benchmark results) $\geq -\theta$	to the central tendency of B.	

To test non-inferiority, the 12 months mean SF-36 PCS result of the T2 Alpha Tibia group will be compared to the mean estimate of the control group, 43.48 points.

To be able to identify an acceptable difference or zone of indifference $(-\theta)$, the lower 90% confidence interval (CI) of the SF-36 PCS result at 12 months post-operative in the control group (Sanders, et al.; Sun, et al.; Chan, et al.) was used as lower limit (lower 90% CI of control is 39.25 points). The maximum acceptable difference in the negative direction is 4.23 points.

Based on the underlying distribution of the data and the result of the normality assessment, either the parametric one-sample t-test or the non-parametric one-sample sign test will be used to compare the 12 months post-operative SF-36 PCS result of the T2 Alpha Tibia group against the value of 39.25 points (mean of control - θ or 43.48 – 4.23 = 39.25 points).

3.1.2. Secondary Analyses

For efficacy/performance, bone consolidation will be assessed by 12 months as measured by Investigator assessment. For Safety, the incidence of device-related adverse events/incidents by 12 months will be monitored through collection and analyses. Both analyses will be part of the final report.

Furthermore, device related adverse events/incidents and the time to (earliest) Device Related Adverse Events/incidents will be analyzed as well. Considered variables, the level of measurement and the planned analysis steps are listed in detail in the SAP.

3.1.3. Additional Analyses

Additional Analyses are outlined in the subsequent sections. Analysis details (variables, level of measurement, planned steps) are listed in-depth in the SAP.

• Weight-bearing status

The weight bearing status will be evaluated and analyzed at the pre-operative visit and at 3 months, 6 months and 12 months. The within subject changes from visit to visit will be analyzed in addition. This analysis will be part of the final report.

External Support

The status of the subject using external support will be evaluated at the pre-operative visit and at 3 months, 6 months and 12 months. The within subject changes from visit to visit will be analyzed in addition. This analysis will be part of the final report.

o Mortality

For analysis of the time to death or mortality, the Kaplan-Meier method will be used. The times between the date of surgery and the date of the 12 months assessment will be used together with the times between date of surgery and the date of death. This analysis will be part of the final report.

• **Reoperation**

For analysis of the time to the reoperation, the Kaplan-Meier method will be used. The times between the date of surgery and the date of the 12 months assessment will be used together with the times between date of surgery and the date of reoperation (earliest reoperation in case that one subject experienced more than one reoperation). This analysis will be part of the final report.

• SF-36 Total Physical Score – Within subject changes by visit

The within subject score changes of the SF-36 Total Score from visit to visit will be analyzed to help identify the changes on the subject level. This analysis will be part of the final report.

3.2. SAMPLE SIZE

The 12 months post-operative results for subjects implanted with the T2 Alpha Tibia Nail will be compared to a historical group and results reported by Wang, et al. (2017); Sanders, et al. (2014); Sun, et al. (2016); and Chan, et al. (2016) will serve as the control group for the T2 Alpha Tibia Nail subjects.

Hypotheses were developed to allow for a comparison of 12 months post-operative SF-36 Physical Component Summary (PCS) results and 12 months effectiveness/performance between these two populations.

Benchmark and Objectives for Planned Research				
Endpoint	Non-inferiority related to the SF-36 Physical Component Summary (PCS) for subjects undergoing infrapatellar (IP) and/or suprapatellar (SP) tibia nailing at 12 months post-operative compared to the pooled literature control.			
Estimated drop- out rate	20% Source: "Stannard et al: Functional Outcome Following Intramedullary Nailing of the Tibia. A Prospective Randomized Comparison of Piriformis Fossa and Greater Trochanteric Entry Portals JBJS 2011" Stannard et al. reported a lost to follow up rate of 19.6% (11/56). Note: The source of Stannard et al. was used for T2 Alpha Tibia as well as it represents a worst-case drop-out rate.			

Results as reported by Benchmark

Non-inferiority related to the SF-36 Physical Component Summary (PCS) for subjects undergoing infrapatellar (IP) or suprapatellar (SP) tibia nailing at 12 months post-operative.

The results from the sources Chan et al, Sanders et al., and Sun et al. were pooled to determine overall two-sided 90% confidence intervals of the mean SF-36 PCS (physical) and mean SF-36 MCS (mental) scores.

Note: The results reported by Wang et al. seemed to be based on a different calculation method for the determination of the SF-36 scores and it was not possible to evaluate, what exactly was done by the authors. The score values reported by Wang et al. are much higher compared to what was normally reported in the literature and what was defined in country specific weights and coefficients. Wang et al. reported median

score values whereas the other authors reported means. As summary score results usually tend to deviate from normality, means and medians might differ significantly. Therefore, the results reported by Wang et al. were not included into the pooled analysis.

Source	Subgroup	Mean SF36- PCS	Mean SF36- MCS	Pooling
Chan et al.	IP	38.00	47.00	included
Chan et al.	SP	46.00	47.00	included
Sanders et al.	SP	40.80	46.00	included
Sun et.al.	SP	49.41	44.71	included
Sun et.al.	IP	43.21	43.81	included
Wang et.al.		79.10	77.00	excluded

Summary of explorative analysis is listed below:

Descriptives

			Statistic	Std. Error
SF-36 PCS Physical at 12	Mean		43,4840	1,98495
months post-op	90% Confidence Interval	Lower Bound	39,2524	
	for Mean	Upper Bound	47,7156	
	Median		43,2100	
	Std. Deviation		4,43849	
	Minimum		38,00	
	Maximum		49,41	
	Range		11,41	
	Interquartile Range		8,31	
SF-36 PCS Mental at 12	Mean		45,7040	,63333
months post-op	90% Confidence Interval	Lower Bound	44,3538	
	for Mean	Upper Bound	47,0542	
	Median		46,0000	
	Std. Deviation		1,41617	
	Minimum		43,81	
	Maximum		47,00	
	Range		3,19	
	Interquartile Range		2,74	

As the mean physical score (PCS) was slightly lower, it was used for the sample size calculation.

For the clinical investigation the one-sided 95% confidence interval will be applied.

Acceptance Criteria for S	Sample Size Calculation			
Significance Level (a)	0.05 (5%)			
Power (1-β)	0.80 (80%)			
Confidence Interval (CI)	0.95 (95%)			
Tails	1			
Path	Non-inferiority T2 Alpha Tibia (A) ≥ Benchmark (B, pooled	benchmark results)		
Hamadhasan Dain	Null (H ₀)	$A - B < -\theta$		
Hypotneses Pair	Alternative (H ₁)	$A - B \ge -\theta$		
Benchmark Timepoint	12 months post-operative			
Benchmark Mean	43.48 points SF-36 PCS at 12 months (IP an	d SP together)		
	No standard deviation results were given by Wang et al.	Chan et al., Sanders et al. nor by		
Benchmark Std. Dev.	• Only Sun et al. reported standard deviations at 12 months postoperative for SF-36 PCS of 6.27 for the SP and of 6.52 for the IP subgroup			
	As a worst-case, the double standard deviation for the sample size calculation $(2 * 6.52 = 13)$	on reported by Sun et al. was used 3.04 points)		
Benchmark 90% CI of Mean	Lower 90% CI: 39.25 (two-sided 90% CI e	quals a one-sided 95% CI)		

	Upper 90% CI: 47.72
Margin (-0)	Lower 90% CI of Benchmark: 39.25
Software Used	IBM SPSS Sample Power V3.0

IBM SPSS Sample Power Output

One goal of the proposed clinical investigation is to test the null hypothesis that the population mean is 39.25. The criterion for significance (alpha) has been set at 0.050. The test is 1-tailed, which means that only an effect in the expected direction will be interpreted.

With the proposed sample size of 61 subjects, the clinical investigation will have power of 80.0% to yield a statistically significant result.

This computation assumes that the population from which the sample will be drawn has a mean of 43.48 with a standard deviation of 13.04. The observed value will be tested against a theoretical value (constant) of 39.25.

This effect was selected as the smallest effect that would be important to detect, in the sense that any smaller effect would not be of clinical or substantive significance.

A second goal of this clinical investigation is to estimate the mean in the population. On average, a clinical investigation of this design would enable us to report the mean with a precision (95.0% confidence level) of plus/minus 2.77 points.

The precision estimated here is the median precision. Precision will vary as a function of the observed standard deviation (as well as sample size), and in any single clinical investigation will be narrower or wider than this estimate.

- Eile View Option	ns Tools Scenarios	Help	- 2 .			_181
Group	Population Mean	Standard Deviation	N of Cases	Standard Error	95% Lo w er	95% Upper
T2 Alpha Tibia IP & S	P 43,48	13,04	61 🔆	1,67	40,71	46,25
Lower Cr bound or be		Ę.				
Alpha= 0,050, Tails= 1		l		F	² ower = 0,805	
Alpha= 0,050, Tails= 1	ver	! 	x	F	⁹ ower = 0,805	
Alpha= 0,050, Tails= 1 Summary - Pov For the given effe constant of 39,22 is 0,805.	ver ct size (population mean= 4 5), sample size (61), and al	43,48, tested ag pha (0,050, 1-tai	ainst a led), power	F	² ower = 0,805	
Alpha= 0,050, Tails= 1 Summary - Pov For the given effer constant of 39,21 is 0,805. This means that 8 effect, rejecting th The test is one-ta direction can be s	ver tot size (population mean= 4 5), sample size (61), and al 1% of studies would be exp ne null hypothesis that the p illed, which means that only statistically significant.	43,48, tested ag pha (0,050, 1-tai pected to yield a opulation mean i an effect in the r	ainst a led), power significant s 39,25, expected	ŗ	⁹ ower = 0,805	

Estimated drop-out rate is 20% which leads to the requirement of enrolling additional 13 subjects into the clinical investigation.

Sample Size	Overall number of subjects to be enrolled: 74 subjects (rounded up to 80 subjects)

Table 3.2: Sample Size Justification

4. Methods

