With the proposed sample size of 61 subjects, the clinical investigation will have power of 80.0% to yield a statistically significant result.

This computation assumes that the population from which the sample will be drawn has a mean of 43.48 with a standard deviation of 13.04. The observed value will be tested against a theoretical value (constant) of 39.25.

This effect was selected as the smallest effect that would be important to detect, in the sense that any smaller effect would not be of clinical or substantive significance.

A second goal of this clinical investigation is to estimate the mean in the population. On average, a clinical investigation of this design would enable us to report the mean with a precision (95.0% confidence level) of plus/minus 2.77 points.

The precision estimated here is the median precision. Precision will vary as a function of the observed standard deviation (as well as sample size), and in any single clinical investigation will be narrower or wider than this estimate.

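### The hypotheses compare T2 Alpha with an estimated benchmark (A − B), but the test and power treat 39.25 as an exact constant, so the stated 5% alpha and 80% power hold only for a fixed goal of 39.25

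*SAP*

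**What the plan says.** SAP 3.1.1 and 3.2, and Protocol 11.1 and 11.3.2, set H0 as A − B < −θ and H1 as A − B ≥ −θ, with A the T2 Alpha Tibia result and B the pooled benchmark. SAP 3.2 describes a comparison of two populations. SAP 3.1.1 calls 43.48 an estimate of the control mean and notes that sample results only estimate population values. The descriptive table in SAP 3.2 gives the benchmark mean a standard error of 1.985 and a 90% interval of 39.25 to 47.72.

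The margin comes from that interval: "The maximum acceptable difference in the negative direction is 4.23 points". The Margin row of the sample-size table, however, gives −θ as "Lower 90% CI of Benchmark: 39.25".

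The planned test (SAP 3.1.1 and 6.6) is a one-sample t-test, or a one-sample sign test if normality fails, against 39.25. On power, SAP 3.2 says: "This computation assumes that the population from which the sample will be drawn has a mean of 43.48 with a standard deviation of 13.04". It continues: "The observed value will be tested against a theoretical value (constant) of 39.25". The settings are "The criterion for significance (alpha) has been set at 0.050", one-tailed, and the result is "With the proposed sample size of 61 subjects, the clinical investigation will have power of 80.0% to yield a statistically significant result". Protocol 11.1 repeats the power statement.

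The conclusion table in Protocol 11.3.2 reports a significant result as T2 Alpha Tibia being at least equal to the control. The Synopsis and Protocol 8.1 word the primary endpoint as non-inferiority to the benchmark literature.

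**The concern.** The stated hypothesis and the test do not match. If B is the unknown mean of a control population, the difference A − B has two sources of error, and the one-sample test counts only the trial's own. The omitted one is the larger: 1.985 for the benchmark against 1.67 for the trial at the planning SD.

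The benchmark's uncertainty does enter the plan once, through the margin, but there it lowers the bar. The margin is a t quantile times the benchmark standard error, so a less precise benchmark gives a wider margin and an easier pass. That does not protect against having misjudged the control.

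At stake is the final claim. Non-inferiority to the control at 5% is a stronger statement than a mean PCS above 39.25 at 5%, and only the second follows from the planned analysis.

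**Working it through.** **Inputs.** From SAP 3.2: five pooled arm means of 38.00, 46.00, 40.80, 49.41 and 43.21; n = 61; planning SD 13.04, which is twice the reported 6.52; one-sided alpha 0.05. From SAP 3.1.1: margin 4.23 and test value 39.25.

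**1. Benchmark.** Mean 43.484, SD 4.438. SE = 4.438/√5 = 1.985. The 95% quantile of t on 4 df is 2.132, and 2.132 × 1.985 = 4.23. The 90% interval is 39.25 to 47.72. This reproduces the plan's table and margin.

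**2. The plan's power.** One-sample t-test of 43.48 against the constant 39.25, SD 13.04, n = 61: noncentral t gives 0.805, matching the software output. For a fixed goal the plan's arithmetic is right.

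**3. Planned rule read as a test of A − B.** Hold the margin at 4.23 and let both estimates vary.

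- Trial SE: 13.04/√61 = 1.670.
- The rule passes when the observed mean exceeds 39.25 by more than t(0.95, 60 df) × SE = 1.671 × 1.670 = 2.789.
- SE of the estimated difference: √(1.670² + 1.985²) = 2.594.
- False-positive rate at A − B = −4.23: P(Z > 2.789/2.594) = P(Z > 1.075) = 0.141.
- Power at A = B: P(Z < (4.23 − 2.789)/2.594) = P(Z < 0.556) = 0.711.

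A simulation of the t-test with 400,000 replicates gave 0.142 and 0.712.

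With SD 6.52, the trial SE is 6.52/√61 = 0.835, the critical distance 1.395 and the combined SE 2.153. The false-positive rate is P(Z > 1.395/2.153) = 0.259. Power at A = B is P(Z < (4.23 − 1.395)/2.153) = 0.906.

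**4. Sensitivity to the benchmark SE (n = 61).** The values 0.5 and 1.0 are assumptions; the documents give only 1.985. Where two figures appear, the first uses the t critical value and the second the normal one.

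| SD | Benchmark SE | False-positive rate at A − B = −4.23 | Power of planned rule at A = B |
|---|---|---|---|
| 13.04 | 0 (fixed goal) | 5% | 80.5% |
| 13.04 | 0.5 | 5.5–5.8% | about 80% |
| 13.04 | 1.0 | 7.6–7.9% | 77–78% |
| 13.04 | 1.985 | 14.1–14.5% | 71–72% |
| 6.52 | 1.985 | about 26% | about 91% |

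**5. Given a particular true benchmark.** The rates in steps 3 and 4 average over benchmark error. With SD 13.04 and n = 61, a device exactly 4.23 points below the true benchmark passes with probability 0.2% if that benchmark is 41.5, 5% if it is 43.48, and 81% if it is 47.72, the plan's own upper limit.

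**The case against.** The strongest reply is that B is simply the published number 43.48. Then A − B ≥ −4.23 is the same statement as A ≥ 39.25, and 5% and 80.5% both hold. The plan gives this conversion openly in SAP 3.1.1 and calls 39.25 a constant in 3.2. The reply is right about the test. It does not settle the hypothesis, because the same documents call 43.48 an estimate, print its standard error and interval, and describe two populations. If a fixed goal is meant, the hypotheses and conclusions should say so.

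The second reply, that 1.985 is rough, stands. It comes from five unweighted arm means, two pairs of which share a study. Within both pairs the suprapatellar mean is the higher, so some of the spread may reflect approach rather than sampling error around one benchmark. Arm sizes are not given, so a better figure cannot be derived. Step 3 also holds the margin fixed while letting the benchmark vary, although both come from the same five values. The sizes are therefore indicative.

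A reader might infer that power is really 46–49%. Those figures belong to a different test, one that carries the benchmark error at SD 13.04 (0.494 by normal approximation, 0.455 by Satterthwaite t on 11.3 df). The planned rule has about 71% at that SD and about 91% at 6.52, so the documents do not support a general statement that its power is far below 80%.

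**Conclusion.** The mismatch is real and should be corrected in both documents. The stated alpha and power hold for a fixed goal of 39.25 and not for A − B with B an estimated control mean. Under that second reading, with the margin fixed at 4.23, n = 61, and the five arm means treated as a sample with SE 1.985, the planned rule's false-positive rate is about 14% at SD 13.04 and 26% at SD 6.52. Its power at A = B is about 71% and 91%.

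The size depends on the benchmark SE. At SD 13.04 an SE of 0.5 to 1.0 brings alpha down to about 6–8% and leaves power at about 77–80%. Some inflation of alpha remains for any SE above zero.

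It would be tempting to conclude that the sample-size calculation is wrong or the trial too small. The documents do not support that: the calculation reproduces for the test it describes. The fault lies in what a pass is said to show.

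**What to change.** In both documents:

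1. Restate H0 and H1 as a one-sample performance goal on 12-month PCS: at or below 39.25 against above 39.25. Specify the mean for the t-test, and say that the fallback sign test addresses the median. Tie the 5% alpha and 80% power to this goal.
2. Change the conclusion table in Protocol 11.3.2, and the primary endpoint wording in the Synopsis, Protocol 8.1 and the matching text of SAP 3.1.1, so that a pass is reported as exceeding the 39.25 performance goal, not as non-inferiority to the control at 5%.
3. Correct the Margin row so that −θ is −4.23 and 39.25 is labelled as the test value.
4. Add one supportive, non-decisional estimate of A − 43.48 with a one-sided 95% bound, using √(s²/n + 1.985²) and Satterthwaite degrees of freedom (about 11 at the planning values). Note that 1.985 is approximate.

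The cost is wording plus one calculation. The formal claim becomes narrower, and the supportive interval will be wider than the one-sample interval. Threshold, test and sample size are unchanged. The rewording does not itself supply a clinical justification for 39.25.

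### The 4.23-point margin is the confidence half-width of five literature means, not a clinical margin, and passing a test against 39.25 does not show a PCS equal to or better than the 43.48 benchmark

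*SAP*

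**What the plan says.** SAP 3.1.1 and CIP 11.3.2 take the lower limit for the device from "the lower 90% confidence interval (CI) of the SF-36 PCS result at 12 months post-operative in the control group". That limit is 39.25 and the control mean is 43.48, hence "The maximum acceptable difference in the negative direction is 4.23 points". The interval is computed in SAP 3.2 and CIP 11.1 from five arm means in three publications, each counted as one unweighted observation.

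The sample size assumes that the population "has a mean of 43.48 with a standard deviation of 13.04", and adds: "The observed value will be tested against a theoretical value (constant) of 39.25". Under the same software output both documents state: "This effect was selected as the smallest effect that would be important to detect", on the ground that "any smaller effect would not be of clinical or substantive significance".

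Success is worded as a PCS result at least as high as the benchmark in the CIP synopsis and 8.1. CIP 11.3.2 and SAP 3.1.1 explain non-inferiority as a result at least as good as the control. The decision table in CIP 11.3.2 translates p ≤ 0.05 into T2 Alpha Tibia ≥ Control.

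**The concern.** A non-inferiority margin should state how large a deficit is acceptable, for a reason that concerns patients. Here it measures how much five published means scatter and how few they are. Calling the result the smallest clinically important effect gives it a meaning that its derivation cannot supply.

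The second problem is the conclusion. Rejecting the null against 39.25 supports a PCS above 39.25, that is, not more than 4.23 points below the literature mean. The plan would report this as equal to or better than 43.48. A reader of the final report would take away a comparison that was not made, backed by a claim of clinical relevance that was not established.

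**Working it through.** **Inputs.** Arm means 38.00, 46.00, 40.80, 49.41 and 43.21 (SAP 3.2, CIP 11.1). Planning SD 13.04, which is twice the larger reported SD of 6.52. One-sided α 0.05. N = 61 evaluable. Enrolment 80 with 20% drop-out, so 80 x 0.80 = 64 evaluable.

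**1. The margin.** Mean 43.484; SD 4.4385; SE = 4.4385/√5 = 1.985; t(0.95, 4 df) = 2.132. Half-width = 2.132 x 1.985 = 4.23; lower limit 39.25. This reproduces the plan's table. No clinical quantity enters.

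**2. The sample size.** For a one-sample, one-sided t-test the noncentrality is 4.23 x √61/13.04 = 2.53, which gives power 0.805 at N = 61. The plan's figure is reproduced.

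**3. Lowest observed mean that passes, 64 evaluable.** 39.25 + t(0.95, 63 df) x SD/√64, with t = 1.669.
- SD 6.52: 39.25 + 1.669 x 0.815 = 40.6.
- SD 13.04: 39.25 + 1.669 x 1.63 = 42.0.

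Both lie below 43.48.

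**4. Probability of passing, 64 evaluable (noncentral t).** A device 2.5 points below benchmark has true mean 40.98, which is 1.73 above 39.25. One 3 points below has true mean 40.48, which is 1.23 above.

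| True deficit | SD 6.52 | SD 13.04 |
|---|---|---|
| 2.5 points | 0.68 | 0.28 |
| 3 points | 0.44 | 0.18 |
| 4.23 points | 0.05 | 0.05 |

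**5. How the rule behaves.** Hold the benchmark mean at 43.48 and the between-arm SD at 4.44. Three arms would give a margin of 7.48, four 5.22, five 4.23 and ten 2.57. With five arms, half the scatter gives 2.12 and one and a half times the scatter gives 6.35. In the actual data the mean moves too:

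| Arm dropped | Mean | Margin | Threshold |
|---|---|---|---|
| 38.00 | 44.86 | 4.36 | 40.49 |
| 46.00 | 42.86 | 5.72 | 37.14 |
| 40.80 | 44.16 | 5.68 | 38.48 |
| 49.41 | 42.00 | 4.01 | 37.99 |
| 43.21 | 43.55 | 6.03 | 37.53 |

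The threshold falls in four of five cases and rises in one. The margin widens in four and narrows slightly in one.

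**The case against.** The derivation is disclosed: both documents say where 39.25 comes from and that the test is against that constant. A literature-derived threshold can be a reasonable goal for a single-arm post-market study. The threshold is fixed in advance and the primary analysis runs once, so it cannot drift with the data. The clinical-importance sentence stands under the sample-size software output and describes the effect to detect, while the margin section itself makes no clinical claim. Deficits of 2.5 or 3 points lie inside the declared margin, so passing with them is not a type I error, and at the margin itself the pass rate is 5%. The 12-month mean with its 95% interval is already planned (SAP 3.1 and Table 6.5.2).

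All of this stands, and it limits the point to justification and wording. It does not rescue either. The effect to detect and the margin are the same 4.23 points, so the unsupported sentence attaches to both. Disclosing the threshold does not make a conclusion of at least equal to control follow from it.

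Two stronger readings are tempting. A reader might infer that scarcer or more scattered literature always makes the test easier to pass. That needs a fixed benchmark mean; dropping 38.00 raises the threshold to 40.49. A reader might also show how unstable the rule is by adding back the source with a score of 79.10. The plan excludes that source for stated reasons (a different scoring method, and medians instead of means), so the exercise says nothing about the plan's benchmark.

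**Conclusion.** The point holds as a fault of justification and of conclusion wording. The margin equals a confidence half-width to the second decimal, neither document offers a clinical basis for it, and the statement that it is the smallest important effect is contradicted by the plan's own derivation. The success wording and the CIP decision table do not follow from a test against 39.25.

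The size depends on the SD. At 6.52, the larger of the two SDs reported at 12 months, observed means down to about 40.6 would be declared equal or better; at the planning value of 13.04, down to about 42.0. The chance that a device 2.5 points worse passes ranges from 0.68 to 0.28 accordingly. These figures assume 64 evaluable subjects, approximately normal scores and the t-test branch of the plan; the sign test was not modelled.

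A reader might infer that 4.23 points is clinically too large, or that the sample size is wrong. The documents support neither: they contain no clinical margin to compare with, and N = 61 is correct for the stated inputs. For the same reason, a sensitivity test at a clinical margin is a debatable design preference and is not part of this point.

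**What to change.** Make the same edits in the CIP and the SAP.

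1. In SAP 3.2 and CIP 11.1, delete the sentence on the smallest important effect.
2. In SAP 3.1.1 and CIP 11.3.2, state that 39.25 is a performance goal derived from the literature (the lower one-sided 95% limit of the mean of five arm means) and that 4.23 is not a clinically derived margin.
3. Reword the success criterion in the CIP synopsis, CIP 8.1 and 11.3.2 and SAP 3.1.1, and the CIP 11.3.2 decision table, as: mean 12-month PCS above 39.25 (not more than 4.23 points below the literature mean). The other row of the table should say that this was not shown, since failure to reject does not establish that the device is below control.
4. In the final report, give the observed difference from 43.48 with its confidence interval beside the test.

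The primary test, threshold and sample size stay as they are, and no further subjects are needed. The cost is editing two documents, one line in the final report, and a success claim less favourable to the device.
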